### 10.2 Secondary study parameter(s)

Similarly to the primary outcome measure, ANOVAs will be conducted for the secondary outcome measures with regard to expectancy effects on histamine evoked itch, scratching behavior, and genotype. Additionally, Pearson correlation coefficients will be calculated between the individual characteristics and the expectancy effects on itch.

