## Secondary objectives:

Secondary goals are to explore:

- a) the itch related expectancy effects on scratching behavior
- b) the itch related expectancy effects regarding itch evoked by histamine iotophoresis
- c) the role of individual characteristics (e.g., optimism) on (the modifiability of) expectancy effects
- d) the role of 5-HTTLPR genotype and other genetic variants on (the modifiability of) expectancy effects

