### 4.4 Sample size calculation

The required sample size was calculated, in agreement with a statistician ([name], Radboudumc), based on our previous study with a comparable design [25]. Such as in the present study, in our previous study a comparison was made between a positive expectation induction by conditioning and verbal suggestion and a control group. In this study an average placebo effect of 0.86 (SD = 0.59) and 0.32 (SD = 0.79) was found in the *conditioning with verbal suggestion group* and the *control group*, respectively (effect size of d = 0.78). Based on these means and standard deviations, sample size calculations were done using G\*power 3.1. We simplified the analyses of the main hypotheses, Univariate analyses of variance (ANOVA's) with Dunnett contrasts, into two two-tailed independent samples t-tests (i.e., comparing the positive expectation induction group with the negative expectation induction group and the neutral expectation induction group separately) using a Bonferroni correction. For these t-tests, the means and standard deviations of the most conservative comparison in the present study were used, i.e., of the positive expectation induction with the neutral expectation induction. With an effect size of d = 0.78, an alpha of 0.025 and a desired power of 0.80, this resulted in an estimated total sample size of 33 participants per group.

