#### 8. METHODS

## 8.1 Study parameters/endpoints

#### 8.1.1 Main study parameter/endpoint

The main study endpoint is the level of itch (VAS scores) evoked by the electrical stimuli associated with the conditioned cues in comparison to the neutral cues in the testing phase of part II of the experiment. It is investigated whether nocebo effects (negative expectation effects) can be modified by a positive expectation induction by conditioning and verbal suggestion (low-itch expectation induction) (group 1), resulting in lower itch VAS scores than a repeated negative expectation induction (high-itch expectation induction) (group 2), or neutral procedure (neutral expectation induction) (group 3).

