## 8.1.2 Secondary study parameters/endpoints

The secondary study endpoints of the present experiment are: a) the scratching behavior of the participants, b) the levels of itch (VAS ratings) induced by histamine iontophoresis after displaying the conditioned cue, c) the scores on several questionnaires measuring individual characteristics related to expectancy effects, d) the 5-HTTLPR genotype and possibly also other genetic variants.

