### 8.2 Randomisation, blinding and treatment allocation

After part I, in which all participants are exposed to the same procedure, in part II participants will be randomly allocated to one of three experimental groups (see section 3. Study design and Fig 1.). We will use a single blind design: Since the instructions given to the subjects differ in accordance with the group the subjects are allocated to, only subjects will be blinded for the randomization to different groups. No indications for breaking the randomization code are indicated.

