#### Neutral expectation induction

In the neutral group, participants will not receive a conditioning procedure or verbal suggestions; the different colored lights are randomly shown with previously defined random stimuli intensities and participants are merely told that a colored cue will indicate the start of a new stimulus.

Participants are asked to rate their levels of itch on a Visual Analogue Scale (VAS) ranging from 0 (no itch at all) to 10 (worst itch imaginable) after each stimulus. Additionally, participants are videotaped to record scratching behavior of the participants during the experimental sessions.

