#### 10. STATISTICAL ANALYSIS

### 10.1 Primary study parameter(s)

All variables are continuous. Descriptive statistics (means, standard deviations, etc.) will be calculated of all relevant variables. Variables will be checked for outliers and skewness as these can severely limit the usefulness of the mean as measure for location.

In consultation with the statistician associated with the study ([name]), our main hypothesis, that the induced levels of itch (VAS) will be lower after a positive expectation induction (low-itch expectation induction) (group 1), in comparison to a negative expectation induction (high-itch expectation induction) (group 2), or neutral expectation induction (group 3), will be tested in an ANOVA using Dunnett contrasts for comparing the expectancy effect on itch in group 1 with the effect in group 2 and group 3.

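### Section 10.2 compares scratching between groups without adjusting for the Part I scratching filmed before randomisation; the ANOVA is unbiased, but may lose precision, depending on how scratching is defined

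*Protocol*

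**What the plan says.** The first secondary objective (section 2) is to explore "the itch related expectancy effects on scratching behavior". Section 8.1.2 lists the endpoint only as "a) the scratching behavior of the participants", with no metric, phase or cue contrast.

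Section 10.2 says that "ANOVAs will be conducted for the secondary outcome measures with regard to expectancy effects on histamine evoked itch, scratching behavior, and genotype", and that this follows the primary outcome. The primary model in section 10.1 is an "ANOVA using Dunnett contrasts for comparing the expectancy effect on itch in group 1 with the effect in group 2 and group 3". Neither section names a covariate.

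On data collection, section 8.3 says "participants are videotaped to record scratching behavior of the participants during the experimental sessions". Section 3 divides the experiment into three parts and has scratching recorded during the experiment, with no restriction to Part II. On timing, section 8.2 says: "After part I, in which all participants are exposed to the same procedure, in part II participants will be randomly allocated". The design summary also describes a testing phase in Part I, in which both cues are shown with stimuli of medium intensity.

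**The concern.** Part I scratching is a pre-randomisation measure of the endpoint, taken under one common procedure, and the planned model leaves it out. If people differ in how much they scratch and keep those differences within a single visit, an analysis of the Part II level treats this variation as noise. The sample size was set for itch alone, so nothing in the protocol secures precision for scratching.

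Section 1 intends to set the effects on scratching beside those on the itch VAS. An imprecise scratching estimate could then suggest that itch changed and scratching did not, when the study was merely unable to tell.

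**Working it through.** **1. The plan's own figure.** Section 4.4 reports that "an average placebo effect of 0.86 (SD = 0.59) and 0.32 (SD = 0.79) was found" in the induction and control groups. The standardised difference is d = (0.86 − 0.32)/√((0.59² + 0.79²)/2) = 0.54/0.697 = 0.775, which the protocol gives as 0.78. A two-sample t-test (noncentral t, two-sided alpha 0.025, power 0.80) needs 33 per group at either value, with power 0.800 and 0.806. The stated 33 reproduces. It concerns itch; the protocol states no effect size or power for scratching.

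**2. Scratching as a level.** Let rho be the correlation between the Part I and Part II measures within a group. Adjustment multiplies the residual variance by 1 − rho² and costs one degree of freedom (64 becomes 63). The effective effect is d/√(1 − rho²), and the noncentrality is that value times √(33/2) = 4.062. At d = 0.78 and rho = 0.5 the effective effect is 0.78/0.866 = 0.901, and the noncentrality rises from 3.17 to 3.66.

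The documents give neither rho nor a scratching effect size. Both are assumed: d = 0.78 is borrowed from itch, and d = 0.5 is a smaller alternative.

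| rho | 1 − rho² | Power, d = 0.78 | Power, d = 0.5 | n per group for 80% at d = 0.78 |
|---|---|---|---|---|
| 0 (no covariate) | 1 | 0.81 | 0.40 | 33 |
| 0.3 | 0.91 | 0.85 | 0.44 | 30 |
| 0.5 | 0.75 | 0.91 | 0.52 | 25 |
| 0.7 | 0.51 | 0.98 | 0.71 | 18 |

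A three-group simulation (4,000 runs per setting, d = 0.78) agrees. Power went from 0.82 to 0.85, from 0.81 to 0.91, and from 0.82 to 0.98 at rho 0.3, 0.5 and 0.7.

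**3. Scratching as a cue difference.** Write scratching under the conditioned cue as u + e₁ and under the neutral cue as u + e₂, where u is the person's stable level. The difference is e₁ − e₂, so u has dropped out before any model is fitted. The same simulation with this outcome gave power of 0.80 to 0.81 with and without the covariate, so there was no gain. A gain would need the Part I cue difference itself to predict the Part II cue difference, or personal levels that act multiplicatively.

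**4. Which definition applies?** The text supports both.
- Section 8.1.2 reads as a level.
- Section 10.2 copies the primary analysis and speaks of expectancy effects. For itch, section 8.1.1 makes that a within-person contrast: ratings "evoked by the electrical stimuli associated with the conditioned cues in comparison to the neutral cues in the testing phase of part II".
- The same sentence of 10.2 applies the term to histamine itch. Section 8.3 gives each participant one histamine application under one cue, so no within-person cue contrast exists there. The term therefore cannot always mean a cue difference.

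**The case against.** The strongest reply is that the loss depends on an undefined variable. If scratching follows the primary endpoint as a cue difference, stable levels cancel and the tabulated gains do not apply. This stands, and it is why the point is conditional.

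Second, even if responsiveness is a stable trait, a common slope may not capture it. Part I conditions everyone towards high itch, whereas in Part II group 1 is conditioned in the opposite direction and group 2 in the same direction. The Part I to Part II slope for a cue difference could therefore be negative in one group and positive in the other. This also stands. When that case was simulated there was essentially no gain, but no material loss either, so it does not make the adjustment harmful.

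Third, the figures contain no scratching data, and scratch measures may be skewed or have many zeros. The normal-theory power values are therefore indicative only.

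Fourth, covariates for an exploratory endpoint are often left to a statistical analysis plan, and nothing in 10.2 forbids adjustment. That limits the weight of the point. But 10.2 does name the model, and the unused measure follows from the protocol's own design.

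A reader might go further and infer that the ANOVA is invalid, or that chance imbalance between groups of 33 biases it. The documents do not support this: allocation is random, and the standard error already reflects chance imbalance. Nor do they support the inference that power is lost whatever the scratching measure turns out to be.

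**Conclusion.** The point holds as a conditional gain in precision on an exploratory secondary endpoint. A pre-randomisation scratching measure should exist and is not in the planned model. That Part I is filmed is inferred from sections 3 and 8.3, which set no limit on the recording; no sentence names Part I.

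For a level analysis at d = 0.78, the gain is about 4, 10 and 18 power points at rho 0.3, 0.5 and 0.7. At d = 0.5 and rho = 0.5 it is about 12 points. For a cue difference with an additive stable level it is nil, unless the Part I and Part II differences correlate with a similar slope across groups. The change is desirable rather than necessary, and the primary analysis is not affected.

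**What to change.** Define the scratching variable first: its metric, the phase scored, and whether it is a level or a conditioned-minus-neutral difference. Then replace the scratching ANOVA in section 10.2 with wording such as: Scratching in the Part II testing phase will be analysed by ANCOVA, with group as factor and the same measure from the Part I testing phase as covariate, using Dunnett contrasts of group 1 with groups 2 and 3; if the measure is skewed, a transformation or a count model with the same covariate will be used.

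This costs one degree of freedom and the scoring of Part I video by the Part II rule. It needs no new participants, procedures or recordings.

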## 10.3 Other study parameters

Not applicable.

#### 10.4 Interim analysis (if applicable)

Not applicable.

#### 11. ETHICAL CONSIDERATIONS

#### 11.1 Regulation statement

The study will be conducted according to the principles of the Declaration of Helsinki (21-10-2008) and in accordance with the Medical Research Involving Human Subjects Act (WMO).

#### 11.2 Recruitment and consent

Healthy participants will be recruited by advertisement. When subjects show their interest in participating, they will receive adequate written information regarding the study. Subjects will be given one week to consider their decision to participate in the study. When participants arrive at the Leiden University for the day of testing, they will be informed orally about the study and sign the informed consent.

### 11.3 Objection by minors or incapacitated subjects (if applicable)

Not applicable.

#### 11.4 Benefits and risks assessment, group relatedness

Although no direct benefits are expected to be experienced by the participants, no risks are involved with participation in this study. The only burden for participants in the investment of time.

## 11.5 Compensation for injury

The sponsor/investigator has a liability insurance which is in accordance with article 7, subsection 6 of the WMO.

The sponsor (also) has an insurance which is in accordance with the legal requirements in the Netherlands (Article 7 WMO and the Measure regarding Compulsory Insurance for Clinical Research in Humans of 23th June 2003). This insurance provides cover for damage to research subjects through injury or death caused by the study.

- 1. € 450.000,-- (i.e. four hundred and fifty thousand Euro) for death or injury for each subject who participates in the Research;
- 2. € 3.500.000,-- (i.e. three million five hundred thousand Euro) for death or injury for all subjects who participate in the Research;
- 3. € 5.000.000,-- (i.e. five million Euro) for the total damage incurred by the organisation for all damage disclosed by scientific research for the Sponsor as 'verrichter' in the meaning of said Act in each year of insurance coverage.

The insurance applies to the damage that becomes apparent during the study or within 4 years after the end of the study.

A request for dispensation of liability and participants insurance is requested, since participation in the study is without risks other than investment of time (see procedure and methods). This is in line with the medical ethical review committee evaluation of our previous studies (e.g., CMO registration number 2010/ 450).

## 11.6 Incentives (if applicable)

Participants will receive a small monetary reimbursement (€35) and will be compensated for travelling costs (when the travelling distance is > 15 km).

### 12. ADMINISTRATIVE ASPECTS, MONITORING AND PUBLICATION

#### 12.1 Handling and storage of data and documents

Anonymous participant identification codes will be used to link data to participants. The file containing the linking between participant numbers and personal data (e.g., name, date of birth) will be managed by the researchers and data manager and will be locked for access by others. Collected data (e.g., questionnaires, laboratory results, informed consents) will be stored for a period of 15 years.

#### 12.2 Monitoring and Quality Assurance

According to the standard procedures of the data manager, the anonymity of the personal data will be guaranteed and data entry will be checked regularly (the current data monitoring protocol of the department of medical psychology of the Radboudumc will be used ). The monitor of the study will later be appointed.

#### 12.3 Amendments

Amendments are changes made to the research after a favourable opinion by the accredited METC has been given. All amendments will be notified to the METC that gave a favourable opinion.

All amendments will be notified to the METC that gave a favourable opinion. Non-substantial amendments will not be notified to the accredited METC and the competent authority, but will be recorded an filed by the sponsor.

A 'substantial amendment' is defined as an amendment to the terms of the METC application, or to the protocol or any other supporting documentation, that is likely to affect to a significant degree:

- the safety or physical or mental integrity of the subjects of the trial;
- the scientific value of the trial;
- the conduct or management of the trial; or
- the quality or safety of any intervention used in the trial.

All substantial amendments will be notified to the METC and to the competent authority.

Non-substantial amendments will not be notified to the accredited METC and the competent authority, but will be recorded and filed by the sponsor.

#### 12.4 Annual progress report

The sponsor/investigator will submit a summary of the progress of the trial to the accredited METC once a year. Information will be provided on the date of inclusion of the first subject, numbers of subjects included and numbers of subjects that have completed the trial, serious adverse events/ serious adverse reactions, other problems, and amendments.

#### 12.5 End of study report

The investigator will notify the accredited METC of the end of the study within a period of 8 weeks. The end of the study is defined as the last patient's last visit. In case the study is ended prematurely, the investigator will notify the accredited METC within 15 days, including the reasons for the premature termination. Within one year after the end of the study, the investigator/sponsor will submit a final study report with the results of the study, including any publications/abstracts of the study, to the accredited METC.

The sponsor will notify the accredited METC and the competent authority of the end of the study within a period of 90 days. The end of the study is defined as the last patient's last visit.

In case the study is ended prematurely, the sponsor will notify the accredited METC and the competent authority within 15 days, including the reasons for the premature termination.

Within one year after the end of the study, the investigator/sponsor will submit a final study report with the results of the study, including any publications/abstracts of the study, to the accredited METC and the Competent Authority.

<In case the final study report will not be available within one year, another term should be defined including the reasons.>

#### 12.6 Public disclosure and publication policy

<Please mention on the arrangements made between the sponsor and the investigator concerning the public disclosure and publication of the research data.>

In accordance with the CCMO statement on publication policy, the results of this study will be disclosed unreservedly, i.e., regardless of confirmation or disconfirmation of the hypotheses. The results will be submitted for publication in peer-reviewed journals.

## STRUCTURED RISK ANALYSIS

Not applicable.

## 12.7 Synthesis

Not applicable.

